#### Adult clinicians

The focus of the intervention is on delivering feedback reports to physicians caring for inpatients with CAP. Clinicians providing care to patients with CAP on the inpatient medical services, or in the ICU will be included. In addition, we will identify up to 30 clinician stakeholders for semi-structured interviews as part of the user centered design process to develop the feedback reports. Because feedback reports are a novel intervention in the inpatient environment, this stakeholder engagement and formative evaluation are critical elements of this protocol. In addition, all providers will receive a survey to evaluate their perceptions of the intervention post-intervention.

#### **Intervention design and implementation:**

The intervention will consist primarily of an automated prescribing feedback report delivered in aggregate to clinicians. The precise content of the report will be developed with stakeholder feedback, but we anticipate these reports will include such data as: 1) number of patients seen by the prescriber group with the target condition; 2) proportion of patients for which the choice of antibiotic was correct (based on electronic indicators); 3) proportion of patients for which duration of prescribing was correct; and 4) proportion of patients for which both indicators were correct. Clinicians may be provided with patient-level information on prescribing only for patients for whom they prescribed (or supervised the prescribing of) antibiotics.

We will work with our sponsor (the CDC) and key stakeholder champions to engage in a rapid user centered design process to create feedback reports that will fit the prescribing context. In previous work we have found this contributes to greater levels of acceptance by clinicians. First, we will optimize the form of the report (how information is displayed) and how the reports will be delivered to prescribers (e.g. individually via email, embedded in a dashboard, provided verbally and division quality improvement meetings). Second, we will determine appropriate implementation supports that will be needed to accompany the introduction of the feedback reports to each clinical setting. Potential implementation supports will include educational materials for prescribers, communication about the feedback reports to bolster prescriber understanding and trust, and champion-led meetings to ensure that prescribers are aware of the intervention. These activities will be designed with scalability in mind, and so they may be used across diverse settings without negatively impacting operations. Clinician champions will be engaged to inform this intervention as part of the study team, and providers will also be recruited as research subjects to participate in the design process.

We will implement the intervention at the completion of the rapid user centered design process. We will start by launching any educational materials or awareness-building activities as previously described before activating the feedback reports. Following the initial awareness-building activities, we would propose to circulate the antibiotic prescribing feedback reports using the format determined in consultation with stakeholders. In the post-intervention period,

we will assess feasibility and acceptability of the reports and implementation activities. To do this, we will conduct semi-structured interviews with our key stakeholder champions and administer a brief survey to prescribers. The survey will contain demographic questions, attitudinal questions about AS used in our previous research, the Feasibility of Intervention Measure (FIM) and the Acceptability of Intervention Measures (AIM). FIM and AIM have demonstrated strong psychometric properties to determine the extent to which stakeholders believe an intervention is feasible and acceptable. Because inpatient providers may be on clinical service very sporadically, rather than administering the survey at one point in time, we will circulate the survey at multiple time points post-intervention to prescribers who have been on clinical service and have one or more encounters with a CAP patient.

**Data collection:**

Data elements obtained from the EHR include: patient demographics, address to calculate area deprivation index), preferred language, comorbidities (ICD-10 codes), admitting service, provider, antibiotic allergies, all medications for the previous 1 year, all diagnosis codes for the previous 1 year, laboratory testing, radiographic testing, discharge disposition, and ED visits/hospitalizations within 30 days after discharge. Antibiotic use measures specific to the condition (choice of agent and duration of therapy) will also be collected. This data will be extracted from the UPHS data warehouse (Clarity) that stores data from the electronic health record. These data will be used in feedback report generation as well as in outcome assessment.

Data will also be collected during the rapid user centered design process as well as during the intervention period in the form of surveys related to feasibility and acceptability of the intervention. Data collected will include interview and survey responses from individual providers. No direct identifiers will be collected.

Finally, we will measure provider engagement as is feasible, including attendance at educational sessions, interaction with data displays of feedback measures.

**Outcomes:**

For aim 1, we will assess sensitivity and specificity of the electronic definition of CAP and the antibiotic prescribing indicators.

In order to demonstrate the effect of the intervention (aims 2 and 3), we will track appropriateness of antibiotic use based on the key indicators in the automated reports for the selected targeted conditions prior to and following implementation of the stewardship interventions. The following indicators will be assessed:

- 1) Choice of antibiotic therapy: administration of a first-line agent within 48 hours of admission
- 2) Duration of therapy: all antibiotic durations  $\leq$  5 days are classified as appropriate

The primary outcome in this study is appropriate antibiotic use for CAP at the encounter level. If an encounter is associated with appropriate antibiotic use for both metrics, the encounter will be classified in the numerator as “appropriate” antibiotic use. The denominator will consist of all CAP encounters. As a secondary analysis, we will separately analyze appropriate antibiotic choice for CAP and appropriate antibiotic duration for CAP. Additional secondary outcomes include: hospital readmission within 30 days from the index visit, ED or primary care revisit within 30 days of the index visit with a new antibiotic prescription for a different antibiotic.

Finally, we will assess implementation metrics, including provider engagement with the feedback reports, as well as provider responses to interviews and surveys conducted as part of the assessment of feasibility and acceptability of the intervention.

Secondary aim: The same two outcomes of appropriateness (choice of antibiotic therapy and duration of therapy) will be used for this aim.

**Analysis:**

At the level of the encounter, patient-specific variables will be compared in the baseline and intervention periods using chi-squared or Wilcoxon rank-sum testing as appropriate. For the primary analysis, a multivariate logistic regression model will be performed at the encounter level, with the intervention (i.e., baseline period vs intervention period) as the primary binary exposure of interest. Calendar month will be included separately in the model, allowing for adjustment for seasonal variation in antibiotic prescribing. We will additionally analyze these data as a pre-post study with segmented regression analysis. This would allow us to assess the immediate change in the outcomes of interest (i.e., appropriate antibiotic use, reflecting antibiotic choice and antibiotic duration) as well as the slope of change occurring associated with the implementation of the intervention. In this analysis we would also control for potential confounders such as changes in the patient population, census, admissions, nurse staffing, etc.

Secondary aim: At the level of the encounter, differences in proportion of appropriate prescribing will be compared by race, using chi-squared testing. Then multivariate logistic regression will be performed at the encounter level, with race as the primary exposure of interest, incorporating other potential confounders in the model.

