**Aim 3:**

We will conduct a quasi-experimental study in the adult inpatient settings measuring the impact of implementing the feedback reports on appropriateness of antibiotic choice and duration for CAP using the validated indicators. The baseline, pre-intervention period will last approximately up to 24 months and the intervention period will last up to 24 months.

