**Sample size:**

For the chart review/validation components of this study, we estimate needing up to 1500 charts for review.

The primary outcome of the interventional component of this study is appropriate antibiotic use for adults with CAP. In order to be classified as "appropriate," both the antibiotic choice indicator and the duration indicator must be appropriate.

Based on preliminary data, we anticipate including up to up to 10,000 adults with CAP over the four-year study period (24 months pre-intervention and 24 months post-intervention). We estimate that approximately 50% of encounters will be associated with appropriate antibiotic prescribing. To detect an improvement to 60%, we require a sample size of 776 (total in the pre and post periods). Given the projected CAP case numbers, have adequate sample size to detect this difference.

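### The primary before/after model states no allowance for correlation within study months, so its interval is too narrow if months vary beyond season

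*Combined protocol and SAP*

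**What the plan says.** The Analysis section defines the main comparison in these words: "a multivariate logistic regression model will be performed at the encounter level". The exposure in that model is a two-level indicator of when the encounter took place, and the section describes it so: "with the intervention (i.e., baseline period vs intervention period) as the primary binary exposure of interest". The only other term it names for that model is for season: "Calendar month will be included separately in the model, allowing for adjustment for seasonal variation in antibiotic prescribing". A segmented regression is planned in addition, to estimate the immediate change "as well as the slope of change occurring associated with the implementation of the intervention". Neither analysis is given a random effect, a robust or clustered variance, an overdispersion factor or an autocorrelation structure, and no other section supplies one.

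On the design, Study Design, Aim 3 says: "The baseline, pre-intervention period will last approximately up to 24 months and the intervention period will last up to 24 months". No concurrent control is described. The Sample size section says "we anticipate including up to up to 10,000 adults with CAP over the four-year study period", and gives 776 encounters in total as enough to detect a rise from 50% to 60% appropriate use. Alpha, sidedness and power are not stated there. The Data collection section already lists "admitting service, provider, antibiotic allergies" among the extracted fields.

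**The concern.** Exposure is assigned by date, not by encounter. All encounters in a given study month have the same exposure, so whatever makes that month unusual (a respiratory virus wave, a change of house staff, a drug shortage) acts on one side of the comparison only.

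Calendar month must mean the twelve recurring months, because a separate term for every study month would be collinear with period. It therefore takes out what January has in common across years, but not what was peculiar to one January. That remainder adds to the sampling variance of the period effect, while a standard error built on independent encounters leaves it out.

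The primary result is a single period effect without a concurrent comparison. If months do vary beyond season, a null or trivial change could be reported as significant with an interval that is too tight, and the understatement grows with the number of encounters per month.

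**Working it through.** **1. The plan's own figure.** Inputs from the Sample size section: 50% and 60%. Inferred: two-sided 5%, 80% power, equal periods. Pooled two-proportion formula:

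n = [1.960 × √(2 × 0.55 × 0.45) + 0.842 × √(0.25 + 0.24)]² / 0.10² = 387.3, so 388 per period and 776 in total.

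This is an exact match. One-sided 5% gives 610, a continuity correction 816 and 90% power 1,038. The formula assumes independent observations, which agrees with the inferred default for the model.

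**2. Nesting.** Up to 24 + 24 = 48 study months. Maximum accrual is 10,000 / 48 ≈ 208 encounters per month.

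**3. Shared month shocks.** ICC is an assumption. At a proportion of 50%, the month SD is √(ICC × 0.25). Design effect DE = 1 + (208.3 − 1) × ICC. True two-sided error = 2 × [1 − Φ(1.96 / √DE)].

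| Month ICC | Month SD | DE | SE ratio √DE | True error |
|---|---|---|---|---|
| 0.002 | 2.2 pp | 1.41 | 1.19 | 9.9% |
| 0.005 | 3.5 pp | 2.04 | 1.43 | 17.0% |
| 0.01 | 5.0 pp | 3.07 | 1.75 | 26.4% |

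Simulating the planned model (period plus twelve calendar months, no true effect, 48 × 208) gave 10.5%, 17.1% and 26.0%, and 5.0% at ICC 0.

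**4. Shocks independent by hospital.** The Study sites section gives about 36,000, 12,000 and 13,521 annual admissions. Splitting pneumonia volume in that proportion (an assumption) gives shares 0.585, 0.195 and 0.220, whose squares sum to 0.429. Then DE = 1 + (208.3 × 0.429 − 1) × ICC = 1.18, 1.44 and 1.88, and true error is 7.1%, 10.3% and 15.3%. Simulation gave 6.9%, 10.2% and 15.0%.

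**5. Near 776.** With 776 / 48 ≈ 16.2 per month and shared shocks, DE is 1.03, 1.08 and 1.15, and error by formula is 5.3%, 5.9% and 6.8%. Simulations, which are noisier, lie in a range of about 5% to 8%.

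**6. Power at 10,000.** The independent-encounter SE of the difference is √(2 × 0.25 / 5,000) = 1.00 pp. At ICC 0.01 with shared shocks it is 1.75 pp, so 10 pp is 10 / 1.75 = 5.7 standard errors. Simulated power with month-level inference stays above 99.9%.

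**7. Month-level overdispersion (floor 1, t reference).** Fixed terms: intercept, period and 11 month terms, 13 in all, leaving 48 − 13 = 35 df (24 − 13 = 11 for 24 months). At 48 × 208 the error was about 3% to 5% over ICC 0 to 0.01. At 768 encounters and ICC 0, power for 50% versus 60% fell from about 80% to 74% over 48 months, and from about 81% to 68% over 24 months.

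**The case against.** The strongest reply is that every error rate rests on an ICC that the documents do not give, and that the first set also assumes every shock hits all three hospitals alike. Both parts stand. If shocks are hospital-specific the inflation is roughly halved, so the shared-shock figures lie near the upper end for a given ICC. Some inflation remains in either case. Not knowing its size is a reason to let the data estimate it by a method fixed in advance.

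A second reply is that nesting is inferred. That also stands. No section fixes a single start date, awareness activities precede the reports, and the intervention section speaks of introducing reports to each clinical setting. One split transition month is negligible; a staggered start by setting would weaken the argument.

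A third is that segmented regression covers the point. It does not: it is additional to the primary model and has no stated error structure.

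A reader might infer that the trial is underpowered, or that month clustering costs it power near 776. The documents do not support this. At the projected maximum the planned contrast is safe, and near 776 most of the loss in step 7 is the price of the stricter test, since it appears at ICC 0.

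A reader might also infer that prescriber clustering must inflate the error. With an assumed 150 attendings per period and ICC 0.05, stable prescribers gave 5.9% against 6.1% without clustering in the same run. Turnover between periods is what matters (14% with half replaced, 24% with all), and the documents do not say how much there will be.

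**Conclusion.** The concern holds in conditional form. As written, the primary model has no stated allowance for study-month correlation, and its interval is too narrow and its p-value too small if months vary beyond season. At 10,000 encounters over 48 months and an assumed ICC of 0.002 to 0.01, the false-positive rate of a nominal 5% test is about 10% to 26% with shared shocks and about 7% to 15% with hospital-specific shocks.

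This rests on four assumptions: the ICC range, an independent-encounter standard error as the default, a date-defined switch common to all settings, and, for the lower figures, volume split by admissions. The damage is confined to interval width and to small or null effects. The plan should be changed on this point, but neither the design nor the stated sample size is overturned. Confidence is medium because the size depends on a quantity that the documents do not report.

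**What to change.** In the Analysis section, pre-specify one study-month-level variance for the primary period effect. A workable choice is an overdispersion factor estimated from study-month totals and not allowed below 1, with a t reference on the actual number of study months minus the fixed terms (35 for 48 months). Use the same variance handling in the segmented regression.

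Make two additions pre-specified sensitivity analyses, so that the primary test is not left open: a prescriber or service random effect, and an AR(1) model for month-to-month autocorrelation. In the Sample size section, label 776 as the independent-observation figure, with 80% power and two-sided 5% if those were the inputs.

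Cost:
- A few sentences of text and a little more analysis. Provider and admitting service are already to be extracted.
- Wider intervals: the SE is about 1.2 to 1.75 times larger at the assumed ICCs under shared shocks.
- A slightly conservative test if months do not vary.
- Lower power if accrual is near 776, caused by the fix itself (step 7).
- Incomplete protection if months are autocorrelated. At ICC 0.005 over 48 months and assumed autocorrelation of 0.5 or 0.7, the planned model gave 32% or 42% error, overdispersion 15% or 26%, and AR(1) on month proportions about 8% or 11%. This is why the AR(1) analysis should be fixed in advance.

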**Secondary aim:**

We will use the retrospective cohort from aim 1 to assess racial disparities in antibiotic prescribing for CAP. Briefly, we will use the two measures of antibiotic prescribing appropriateness to assess for differences in appropriate prescribing by race, adjusting for other variables.

**Study sites:**Adult

The Hospital of the University of Pennsylvania (HUP) is a 774-bed academic quaternary acute care medical center. There are over 36,000 admissions, 1,500,000 outpatient visits, and 65,000 Emergency Department visits annually.

Penn Presbyterian Medical Center (PPMC) is a 324-bed urban community acute care hospital in West Philadelphia. There are 12,000 admissions, 130,000 outpatient visits, and 31,000 ED visits annually.

Chester County Hospital (CCH) is a 257-bed facility with 13,521 admissions, 425,107 outpatient visits, and 45,317 ED visits annually. The service area is primarily urban and suburban Chester County, Pennsylvania.

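### The primary pre-post logistic model names only period and calendar month: no hospital term, no case-mix terms and no method for correlation within prescriber

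*Combined protocol and SAP*

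**What the plan says.** The Analysis section of the combined protocol and SAP states that "a multivariate logistic regression model will be performed at the encounter level", with baseline versus intervention period as the binary exposure. One further term is named: "Calendar month will be included separately in the model, allowing for adjustment for seasonal variation in antibiotic prescribing". Patient variables are compared between periods by simple tests, but no rule carries the result into the model.

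A segmented regression is then described as an additional analysis, followed by: "In this analysis we would also control for potential confounders such as changes in the patient population, census, admissions, nurse staffing, etc". That list is open-ended, but it names neither hospital nor prescriber. The secondary-aim model on race, in the same section, does promise potential confounders. The primary model has no such clause.

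Other sections describe the setting:
- **Study sites:** three unlike hospitals are pooled. One is a quaternary academic centre of 774 beds, one "is a 324-bed urban community acute care hospital in West Philadelphia", and one a facility of 257 beds.
- **Aim 3:** "The baseline, pre-intervention period will last approximately up to 24 months and the intervention period will last up to 24 months".
- **Adult clinicians:** "Clinicians providing care to patients with CAP on the inpatient medical services, or in the ICU will be included".
- **Data collection:** the extract includes "comorbidities (ICD-10 codes), admitting service, provider, antibiotic allergies". It does not name a hospital field.

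**The concern.** Two separate problems follow if the primary model is run with only the terms it names.

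**Bias.** The comparison is before versus after, with no concurrent control. If the share of encounters from a hospital or patient group changes between periods, and that group differs in appropriate prescribing, the change appears as part of the period odds ratio. Month of year adjusts for season and does not remove it.

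**Precision.** The outcome is a prescriber's decision, and Aim 1 itself asks whether the indicators can be attributed to individual prescribers. Encounters of the same prescriber are therefore likely to be correlated. The model-based standard error ignores this, and can be too small if prescribers, or their habits, differ between periods.

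At stake is how a small positive result is read. A larger sample does not help with bias: the more encounters there are, the more readily a small artefact reaches significance.

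**Working it through.** **1. The plan's own figure.** Sample size gives 50% versus 60% and a total of 776. Alpha, sidedness and power are not stated. A pooled two-proportion test at two-sided 5% with 80% power, equal periods and no continuity correction gives

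n = [1.96·√(2·0.55·0.45) + 0.842·√(0.25 + 0.24)]² / 0.10² = 387.3, so 388 per period and 776 in total.

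This is an exact match. The formula treats encounters as independent, that is, with a design effect of 1.

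**2. Mix shift.** Assume 5,000 encounters per period, a rate near 50% and no true effect. Bias = (gap in rate between groups) × (change in share). SE of the difference = √(4·0.25/N), which is 1.0 point at N = 10,000 and 1.58 points at 4,000. The false-positive rate is that of a two-sided 5% test centred on bias/SE.

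| Gap × share shift (assumed) | Bias | False positives, N = 10,000 | N = 4,000 |
|---|---|---|---|
| 10 points × 2 points | 0.2 point | 5.5% | 5.2% |
| 10 points × 5 points | 0.5 point | 7.9% | 6.2% |
| 10 points × 10 points | 1.0 point | 17.0% | 9.7% |

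**3. How large a hospital shift is credible?** Study sites gives about 36,000, 12,000 and 13,521 admissions, or 59%, 20% and 22% of 61,521. These are a proxy, because CAP shares are not given. For one hospital to gain 10 points of share with the others unchanged, its volume must grow by about 54%, 73% or 67% respectively. A 5-point gain needs 23% to 34%. The upper rows are therefore large for hospital mix alone. Patient mix has no such bound in the documents.

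**4. Prescriber correlation.** Let m be encounters per prescriber per period, and CAC the share of prescriber variance common to both periods. For the pre-post difference,

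DEFF = m·ICC·(1 − CAC) + (1 − ICC), and type I error = 2·[1 − Φ(1.96/√DEFF)].

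DEFF exceeds 1 only when m(1 − CAC) > 1. All inputs below are assumed. At 5,000 encounters per period, m = 10 means 500 prescribers and m = 25 means 200.

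| ICC | CAC | m | DEFF | Type I error |
|---|---|---|---|---|
| 0.05 | 0.5 | 2 | 1.00 | 5.0% |
| 0.05 | 0.5 | 5 | 1.075 | 5.9% |
| 0.05 | 0.5 | 10 | 1.20 | 7.4% |
| 0.05 | 0.5 | 25 | 1.575 | 11.8% |
| 0.05 | 0.95 | 10 | 0.975 | 4.7% |
| 0.05 | 1 | any | 0.95 | 4.4% |
| 0.10 | 0 | 25 | 3.40 | 28.8% |

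**5. Power and large effects.** 776 × DEFF is about 931 at 1.20, 1,222 at 1.575 and 2,638 at 3.40, all well under 10,000. Only a far corner (100 encounters per prescriber, ICC 0.20, no shared variance: DEFF 1 + 99·0.20 = 20.8, or 16,141 encounters) would exceed it. For an observed 10 points, remove 2 points of bias (for example a 20-point gap × a 10-point shift) and inflate the SE by √3.40 = 1.84: 8/1.84 = 4.3 standard errors.

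**6. Cost in precision.** √1.20 = 1.10 and √1.575 = 1.25. A simulation of logistic models (2,000 runs, ICC 0.05, CAC 0.5, no mix shift) gave standard-error ratios of 1.13 at m = 10 and 1.29 at m = 25. Hence about 1.1 to 1.3. With fully stable prescribers the same simulation gave 5.7% type I error where the formula gives 4.4%. That small gap is unexplained, and nothing here depends on it.

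**The case against.** **The model may not be closed.** The word multivariate implies covariates, and the text never says that period and month are the only ones. This stands. A reader might infer that the plan rules out adjustment; it does not. The error rates above describe the model run with its named terms only, which is one reading of an open specification. Even so, with no rule for what else enters, covariates could be chosen after results are seen.

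**Confounders are controlled elsewhere.** The sentence quoted from the end of the analysis plan covers patient population and has an open list. It lessens the patient-mix worry, but its opening words point to the segmented regression just described, which is additional. If both models were meant, the text should say so.

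**Sporadic service cuts both ways.** The plan notes "Because inpatient providers may be on clinical service very sporadically". Few encounters per prescriber lower the design effect: at m = 2 with nothing shared between periods it is 1.05, and type I error is 5.6%. Sporadic service may also mean that different prescribers fill the two periods, which raises it. The documents do not settle which dominates, so the claim that the interval is always too narrow is not supported.

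**A large hospital shift is not expected.** Nothing in the documents predicts one or staggers sites between periods. This stands, and it limits the likely size of the hospital component.

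**Conclusion.** The concern holds as a gap in the primary specification with a conditional consequence. Any unadjusted change in hospital or patient mix that is related to prescribing enters the primary odds ratio. The model-based interval is too narrow when m(1 − CAC) > 1, and otherwise near nominal or slightly conservative.

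The magnitudes are illustrative throughout, because ICC, attending numbers, hospital-specific rates and mix shifts are all assumed. On those inputs the damage runs from negligible (about 5.0% to 5.5% false positives) to material (17% for 1 point of bias, 11.8% for clustering at 25 encounters per prescriber per period).

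Two stronger readings should be resisted. One is that the study is underpowered because 776 ignores clustering: the projected 10,000 encounters absorb that on these inputs. The other is that a finding near the 10-point target could be an artefact of these omissions: at the sizes considered it would survive. The exposure is to a small improvement, of a point or two, being declared significant. The change should be made, but the omission is not fatal to the study.

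**What to change.** Amend the primary model before intervention-period outcomes are analysed:

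1. Enter hospital as a fixed effect.
2. Add a short, named list of pre-treatment case-mix terms from the planned extract: a stated comorbidity index or list, admitting service and antibiotic allergy. Add ICU status at admission only if the field is confirmed and Aim 1 does not remove ICU patients. Keep viral-pneumonia coding for a sensitivity analysis, since a code may be assigned after the antibiotic decision.
3. Use cluster-robust variance (GEE with independence working correlation) by the prescriber unit that Aim 1 finds attributable, with attending of record as the default. The unit needs that step because choice and duration may be decided by different clinicians.
4. Say whether the confounder sentence also covers the primary model.
5. State that 776 assumes independent encounters.

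Possible wording:

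> The primary model will regress appropriate use on period, calendar month, hospital, [named comorbidity index], admitting service and antibiotic allergy, with robust variance clustered by the prescriber unit established in Aim 1 (default: attending of record). The odds ratio is conditional on these covariates and averaged over prescribers.

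The denominator stays as all CAP encounters. The cost is analysis text and code, confirmation that a hospital field is in the extract, and intervals about 1.1 to 1.3 times wider under the illustrative inputs.

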**Study subjects:**

There are two study populations for this study: patients and clinicians.

Patients with community acquired pneumoniaInclusion:

1. Diagnosis of community acquired pneumonia based on ICD-10 diagnostic codes (see appendix 1)
2. Prescribed one or more antibiotic within the first 48 hours of hospitalization AND at least one dose administered between 24 and 48 hours OR discharged within 48 hours on antibiotics
3. Chest x-ray or chest CT within 48 hours of admission

Exclusion

1. Transfer from another healthcare facility
2. Died within the first 48 hours of admission

For the secondary component of Aim 1 in which we compare the electronic definition of CAP and provider selected indication with manual chart review, our eligible patient population will include all adult patients who received at least one dose of doxycycline or azithromycin within the first 48 hours of admission. Patients who die within the first 48 hours of admission will be excluded. A random sample will then be selected for chart review.

Our interaction with patients will be limited to review of existing EHR data. We will have no direct contact with patients. Appropriateness of antibiotic use will be reported on an encounter level; data will be aggregated prior to giving feedback to clinicians, though, clinicians may be provided with information on prescribing only for patients for whom they prescribed (or supervised the prescribing of) antibiotics.

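### The race comparison analyses encounters although race is fixed within patient; if patients contribute repeat CAP encounters with correlated prescribing, the chi-squared test, and the logistic model if run with default standard errors, will understate uncertainty

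*Combined protocol and SAP*

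**What the plan says.** The Secondary aim paragraph fixes the data source: "We will use the retrospective cohort from aim 1 to assess racial disparities in antibiotic prescribing for CAP". The Analysis section then gives two steps, both at encounter level. In the first, "differences in proportion of appropriate prescribing will be compared by race, using chi-squared testing". The second reads "Then multivariate logistic regression will be performed at the encounter level, with race as the primary exposure of interest", with other potential confounders added to the model.

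Race comes from the patient's record; the Data collection section begins "Data elements obtained from the EHR include: patient demographics". The Study subjects section has two exclusions: transfer from another facility, and "Died within the first 48 hours of admission". Neither removes a patient's second or later CAP encounter. The Outcomes section defines the denominator of the primary outcome for the intervention aims as follows: "The denominator will consist of all CAP encounters". It also lists "hospital readmission within 30 days from the index visit" as a secondary outcome, so some patients are expected back in hospital.

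No section names GEE, a random effect, clustered or robust standard errors, or an analysis restricted to first encounters. The plan gives no sample size, power or significance level for the race aim.

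**The concern.** Pearson's chi-squared test treats every encounter as an independent observation, and so does logistic regression with its default standard errors. A patient's antibiotic allergies and comorbidities, which the plan collects, persist from one admission to the next, so positive correlation between that patient's encounters is the natural expectation. Because race is constant within patient, all of those encounters fall in the same race group. The correlation therefore adds to the variance of the race difference, with no within-patient contrast to offset it.

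The aim is to identify disparities. Understated uncertainty makes it easier to declare one, so a borderline finding could be reported with more confidence than the data carry.

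**Working it through.** **The plan's own figure.** The only sample size for a comparison is the total of 776 for the before-after study, to detect 50% versus 60%. It reproduces under two-sided 5% significance, 80% power, pooled variance and no continuity correction. These settings are inferred, because the plan does not state them:

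n per period = [1.96·√(2·0.55·0.45) + 0.8416·√(0.50·0.50 + 0.60·0.40)]² / 0.10² = 387.3, rounded up to 388, so 776 in total.

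This confirms the Aim 3 arithmetic but has no bearing on the race aim, which has no stated figure to check.

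**Inputs for the race aim.** The unit of analysis, the exposure and the eligibility rules come from the sections quoted above. The repeat rate and the within-patient correlation ρ are not in the documents, so both are assumptions.

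**Formulas.** For an exposure that is constant within patient, with m encounters per patient:

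- weighted cluster size m_w = Σm² / Σm
- design effect DEFF = 1 + (m_w − 1)·ρ
- shortfall in the naive standard error = 1 − 1/√DEFF
- actual level of a nominal two-sided 5% test = 2·[1 − Φ(1.96/√DEFF)]

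**Main range.** Two illustrative distributions of encounters per patient:

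- Lower: 88% of patients have one encounter, 9% two, 3% three (12% with repeats). Mean 0.88 + 0.18 + 0.09 = 1.15; mean square 0.88 + 0.36 + 0.27 = 1.51; m_w = 1.51/1.15 = 1.313.
- Higher: 80% have one, 12% two, 5% three, 3% four (20% with repeats). Mean 0.80 + 0.24 + 0.15 + 0.12 = 1.31; mean square 0.80 + 0.48 + 0.45 + 0.48 = 2.21; m_w = 2.21/1.31 = 1.687.

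| m_w | ρ | DEFF | SE too small by | Actual level |
|---|---|---|---|---|
| 1.313 | 0.1 | 1.031 | 1.5% | 5.4% |
| 1.313 | 0.3 | 1.094 | 4.4% | 6.1% |
| 1.687 | 0.1 | 1.069 | 3.3% | 5.8% |
| 1.687 | 0.3 | 1.206 | 8.9% | 7.4% |

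**Wider range.** The same formulas with ρ from 0.05 to 0.5:

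| Patients with repeats | DEFF | Actual level |
|---|---|---|
| 5% with two | 1.005 to 1.048 | 5.05% to 5.55% |
| 10% with two | 1.009 to 1.091 | 5.1% to 6.1% |
| 15% with two, 5% with three | 1.024 to 1.240 | 5.3% to 7.8% |
| 20% with two, 7% with three, 3% with four | 1.041 to 1.413 | 5.5% to 9.9% |

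**Simulation check of the crude comparison.** There were 1,500 patients, 40% in one race group, no true race difference, a beta-binomial outcome with mean 0.5, and 4,000 replicates per setting (Monte Carlo standard error near 5% is √(0.05·0.95/4000) = 0.34 percentage points). The naive test rejected about 4.9% of the time when 10% of patients had two encounters and ρ was 0.1, which cannot be told apart from 5%. It rejected about 10.1% of the time in the heaviest repeat scenario with ρ = 0.5. Across the settings run, patient-clustered standard errors gave 4.8% to 5.8%. The adjusted model was not simulated.

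**The case against.** The strongest reply is that the documents do not show a material number of repeat encounters. No time window is given for the Aim 1 retrospective cohort, and a short window would yield few repeats. The all-encounters denominator is written for the primary outcome of the intervention aims, not for the race cohort. The readmission outcome is not confined to CAP, so it does not establish repeat entries. The Sample size section counts adults while the analysis counts encounters, which leaves the point ambiguous. All of this stands. A reader might infer that the planned p-values and intervals are certainly too favourable; the documents support only a conditional statement.

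Second, a reader might infer that the logistic model is specified wrongly. The plan does not state its standard errors, and naming logistic regression does not rule out clustered ones. Only the chi-squared test, a preliminary step before the adjusted model, is explicit about its method. That also stands, although an analyst following the text as written would reach for default errors.

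Third, allergies and comorbidities are among the collected variables, and the adjusted model may include them. Adjustment would absorb part of the within-patient correlation, so the figures above suit the crude comparison better and probably overstate the effect on the adjusted one.

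Fourth, it is tempting to add that frequently admitted patients distort a group's proportion. That weighting follows from choosing the encounter as the unit. It is a question of estimand rather than an error, and clustered standard errors leave it unchanged.

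Finally, the direction described here rests on positive within-patient correlation and concerns patient-level dependence only. Clustering by prescriber and by the three hospitals is also unaddressed, but race varies within those clusters, so its effect could go either way. It is a separate point.

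What remains is that the plan neither rules out repeat encounters nor says how they would be handled.

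**Conclusion.** The point holds in conditional form and is minor. If patients contribute repeat CAP encounters with positively correlated prescribing, the planned chi-squared test will understate uncertainty about the race difference, and so will the logistic model under default standard errors.

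With 12% to 20% of patients having repeats and a correlation of 0.1 to 0.3, both assumed, standard errors are about 1.5% to 9% too small and a nominal 5% test runs at about 5.4% to 7.4%. Only a borderline result would change. The point concerns an observational secondary aim; the before-after result is a separate matter.

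**What to change.** State in the Analysis section whether repeat encounters are kept. If they are, keep the encounter-level estimand and, for both the crude and the adjusted race comparison, use GEE or logistic regression with standard errors clustered on patient, replacing the plain chi-squared test and default errors. Report the number of encounters per patient by race, so that readers can see how much repetition there is and where it lies. Add a sensitivity analysis on each patient's first encounter, described as answering a slightly different question.

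The cost is a few sentences in the SAP and slightly wider intervals. A patient identifier should already be in the extract, because the Data collection section links a year of earlier medications and diagnoses, and returns within 30 days of discharge. If repeats prove rare, results will barely move.
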